**Study Title:** A feasibility study assessing the inclusion of Physical Activity Promotion to standard care pulmonary rehabilitation and cognitive behavioural therapy in patients with COPD who are anxious and depressed.

**Summary:**

In patients with COPD, daily physical activity is reduced compared with that in healthy age-matched individuals. Furthermore, it is well documented that reduced levels of physical activity in patients with COPD are associated with a faster rate of disease progression, greater risk for exacerbation of COPD (ECOPD), leading to increased rates of hospital admissions and mortality. Global guidelines endorse pulmonary rehabilitation as an integral non-pharmacological component in COPD management. However, while supervised pulmonary rehabilitation programs improve exercise capacity and health related quality of life in people with COPD, these findings have not consistently progressed into improvements in daily physical activity.

Physical activity is a complex health behaviour that is modified by behavioural change interventions such as identification of barriers, goal setting, self-efficacy, motivation, self-monitoring and feedback. Physical activity promotion through interventions, which combine the use of wearable monitors (i.e. pedometers, accelerometers) with goal setting, can increase daily physical activity in COPD patients. A recent systematic review and meta-analysis addressed the addition of physical activity promotion strategies to standard pulmonary rehabilitation, failing to demonstrate consistent improvements in daily physical activity along with improvements in exercise capacity and quality of life. This is principally due to diverse interventions that have lacked an emphasis on individualised goal setting and patient feedback, with only a small number of contact sessions to discuss strategies for consistently improving activity levels and affecting motivation towards behaviour change.

Alongside physical activity promotion, the incorporation of cognitive behavioural modification (CBM) strategies is also important in terms of reversing physical inactivity in COPD. CBM addresses several behavioural barriers including anxiety, depression and physical inactivity, an important component in the management of COPD to improve engagement with pulmonary rehabilitation and physical activity promotion strategies.

Accordingly, we propose to perform a feasibility study assessing patient adherence to a pulmonary rehabilitation programme that concomitantly promotes daily physical activity and behavioural changes. We will compare patients' adherence to pulmonary rehabilitation including physical activity promotion and behavioural changes with pulmonary rehabilitation alone. Our major outcome will be adherence to the combined intervention over 16 sessions of PR.

**Literature background:**

COPD is a debilitating and progressive disease, primarily affecting the respiratory system. In many patients, it also has adverse extra-pulmonary effects, such as skeletal muscle dysfunction and weakness [1]. Pulmonary and skeletal muscle metabolic abnormalities enhance the ventilatory requirement during exercise, resulting in exercise-associated symptoms such as breathlessness and leg discomfort. These symptoms make every day physical activity an unpleasant experience, which many patients try to avoid [2]. Physical activity levels are therefore remarkably lower in COPD patients than healthy age-matched individuals, presenting a major predictor of mortality and hospitalisation in these patients [3]& [4].

Implementation of exercise training as part of Pulmonary Rehabilitation aims to reserve the systemic consequences of COPD, in particular skeletal muscle dysfunction and weakness [2]. Currently pulmonary rehabilitation programs have shown substantial improvements in exercise tolerance; however, these findings have not consistently progressed into improvements in daily physical activity [5]. One reason for this may link to physical activity in COPD being a complex health behaviour [2].

Physical activity promotion is an intervention employed to influence physical inactivity in patients with COPD [5]. The main aim of the intervention is to stimulate patients to increase their daily physical activity levels by incorporating lifestyle activities into daily life. Patients receive counselling in order to modify their behaviour towards enhanced physical activity through the application of a pedometer, which allows patient monitoring and feedback of their daily steps along with frequently adjusted goal setting. Previous research has shown that remote coaching of physical activity (tele coaching) improves daily steps over a three-month period [6]. Studies incorporating physical activity promotion during pulmonary rehabilitation have, however, failed to find consistent improvements in daily physical activity along with improvements in exercise capacity and quality of life [7]. This is principally due to diverse interventions that have lacked an emphasis on individualised goal setting and patient feedback, with only a small number of contact sessions to discuss strategies for consistently improving activity levels and affecting motivation towards behaviour change. No study to date has comprehensively incorporated both a behavioural change intervention (physical activity promotion along with some form of behavioural modification therapy) and pulmonary rehabilitation to facilitate progression of improved physical functioning to enhanced daily physical activity levels. Primarily adherence to the behavioural physical promotion intervention alongside pulmonary rehabilitation has been inconsistent [8]. Consequently, more evidence is required to understand the true benefits of the intervention. The current study aims to provide regular feedback of daily steps (twice weekly), with a pre-intervention interview enabling the research team to understand patient concerns and preferences around daily physical activity. This will provide the healthcare team with information, which can be incorporated into individualised goals, allowing patients to receive physical activity support tailored to their own specific needs, capabilities and daytime habits.

Alongside the physical barriers influencing daily physical activity, the distressing nature of COPD has a significant impact on patients' psychological wellbeing. Major focusing points for COPD patients are the sense of feeling unwell, the inability to perform everyday activities and the emotional consequences of the condition (British Lung Foundation, 2006). These symptoms can promote anxiety and depression, which are prevalent in patients with COPD and are associated with poorer treatment outcomes and reduced survival [9]. Cognitive Behavioural modification (CBM) strategies is a psychological intervention that focuses on understanding how experiences are interpreted. It provides an interaction between thoughts, mood, behaviour and physical sensations, which are intrinsically linked. [10] conducted a small case study involving 10 COPD patients. They used CBM strategies in COPD patients who were anxious or depressed, assessed using the hospital anxiety and depression scale. Techniques used for anxiety included; education on anxiety and COPD, distraction techniques, breathing control and relaxation. These techniques help to break the vicious cycle of anxiety and can reduce patients' distress. Similar techniques for patients suffering mainly from depression include; education about depression and inactivity and planning and recording activities each day, while rating these for achievement or pleasure. These techniques help to break patient inactivity, which can lead to low mood and poor physical condition. A key treatment for depression can involve encouragement to increase activities within the patients' physical capabilities. The study found clinical and statistically significant improvements in anxiety and depression scores and a statistically significant reduction in hospital admissions following CBM strategies [10]. CBM is therefore an important approach to incorporate into COPD management to improve engagement with pulmonary rehabilitation and the effectiveness of a physical activity promotion strategy. [10].

The addition of CBM strategies to structured pulmonary rehabilitation is currently under investigation (TANDEM COPD trial). The feasibility of assessing patient adherence to a pulmonary rehabilitation programme that concomitantly promotes daily physical activity and behavioural changes is still unknown. Accordingly, it is proposed that it is necessary to incorporate standard pulmonary rehabilitation and physical activity promotion along with behavioural modification strategies to induce both functional and behavioural changes including anxiety, depression and physical inactivity.

**Research question:**

The project will investigate whether patients adhere well to an intervention combining standard pulmonary rehabilitation sessions (including exercise training and education), instructions on promoting daily physical activity and behavioural modification strategies to combat anxiety, depression and physical inactivity.

**Aims:**

The primary objective is to investigate patient adherence to the regular use of activity trackers to monitor and adjust daily physical activity levels during the course of a standard pulmonary rehabilitation programme (16 sessions) that includes behavioural modification consultancy sessions.

The secondary aims are to assess:

- Change in physical activity using a validated triaxial accelerometer.
- Mean change in Hospital Anxiety and Depression Score assessed by the HADS questionnaire.
- Mean change in quality of life assessed by St' Georges Respiratory Questionnaire (StGRQ).
- Exercise capacity assessed by the 6-min walking test (6MWT).

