**Key inclusion criteria:**

- 1) COPD confirmed by obstructive spirometry.
- 2) Clinically stable male or female COPD patients aged 40 years or older.
- 3) Optimised medical therapy
- 4) Able to provide informed consent.
- 5) HADS score of 8 or above.

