**Trial Outcomes:**

The primary outcome is to investigate patient adherence to the regular use of activity trackers to monitor and adjust daily physical activity levels during the course of a standard pulmonary rehabilitation programme (16 sessions) that includes behavioral modification consultancy sessions to adopt an active lifestyle.

Secondary outcomes include:

- Change In physical activity at 9 weeks;
- Change in hospital anxiety and depression score at 9 weeks;
- Change in 6MWT at 9 weeks
- Change in QOL at 9 weeks

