### *Health-related Quality of Life:*

[figure not shown]
Quality of Life (QoL) will be assessed at the onset and following completion of the PR program. Patients will be asked to complete different questionnaires in order to evaluate their emotional condition and symptoms. The assessment of QoL will include 2 different questionnaires namely: Hospital Anxiety and Depression Score (HADS), and the St George's Respiratory Questionnaire (StGRQ)). The questionnaires will be administered within 1 week before and within 1 week after the end of the rehabilitation programme.

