## **Statistical plan**

[figure not shown]
Statistical analyses will be supported by standard statistical software (e.g. SPSS, SAS) as required. This is a feasibility study and key outcomes of interest relate to adherence, attendance and drop out rather than clinical outcomes. However, clinical outcome data (steps/day) will be collected and reported to help inform a future randomized controlled trial. Feasibility data will be summarized using standard descriptive statistics, depending on the level of the data (e.g. mean, median, standard deviation, range). Baseline characteristics between groups will be assessed by t-tests for independent samples. Differences between groups across different time points will be assessed by a two-way ANOVA with repeated measures followed by appropriate post-hoc analysis. The Level of significance is set at  $p < 0.05$ .

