**Table 1: Assessment of variables prior to and following the rehabilitation programme**

Visit number (Assessments)	1	2	3	4
	Week 0	Week 1	Week 9	Week 10
Inclusion/Exclusion criteria	x			
Information & Informed consent	x			
Physical examination	x			
mMRC evaluation	x			
Current medication review	x			
Pulmonary Function Assessment		x		
Heart Function Assessment (resting ECG)		x		
BMI (body composition)		x		x
Oximetry & Blood Pressure		x		
6 Minute Walk Test		x		x
Daily Physical Activity Assessment	x		x	x
Quality of Life Assessment		x		x

**Figure 1: Study design** . PA: physical activity; CBM: cognitive behavioural modification, 6MWT: 6-min walk test, HADS: Hospital anxiety and depressions score, StGRQ: St’Georges Respiratory questionnaire.

**Figure 2: Consort Diagram.** PR: pulmonary rehabilitation, CBM: cognitive behavioural modification, PA: Physical activity promotion.

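### HADS selects patients at 8 or above, but only one pre-programme HADS is scheduled; if it is also the baseline, within-arm change is expected to show a fall without any treatment effect

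*Protocol*

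**What the plan says.** - **Entry.** Key inclusion criteria require "HADS score of 8 or above". They do not say whether this is the total score or a subscale, or which administration is used.
- **Outcome.** The Aims list "Mean change in Hospital Anxiety and Depression Score assessed by the HADS questionnaire" and Trial Outcomes list "Change in hospital anxiety and depression score at 9 weeks". Neither names a comparator.
- **Timing in the text.** Health-related Quality of Life makes HADS one of its two questionnaires and states: "The questionnaires will be administered within 1 week before and within 1 week after the end of the rehabilitation programme". That gives one administration before and one after.
- **Timing in Table 1.** The row "Inclusion/Exclusion criteria" is marked only at Visit 1 (Week 0). The row "Quality of Life Assessment", which contains HADS, is marked at Visit 2 (Week 1) and Visit 4 (Week 10), and not at Visit 1.
- **Sequence.** Planned interventions names confirmation of eligibility and baseline assessment as separate steps, both before 1:1 randomisation of 40 patients.
- **Analysis.** The Statistical plan states: "Differences between groups across different time points will be assessed by a two-way ANOVA with repeated measures followed by appropriate post-hoc analysis". Significance is set at p < 0.05.

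**The concern.** These places do not fit together. Eligibility depends on a HADS score and is checked at Week 0, but no HADS is scheduled until Week 1. Either the Week 1 score decides entry, and then also serves as baseline, or entry rests on a HADS that the Protocol never describes.

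The first reading matters because a score chosen for being high tends to be lower when it is measured again. Part of what carried each patient over the cut is measurement error and short-term fluctuation, and that part does not persist. A bare mean change, or the time effect in the repeated-measures ANOVA, would count this fall as improvement. The trial could then report lower anxiety and depression when some or all of the fall comes from the entry rule.

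**Working it through.** **No figure to reproduce.** The Protocol gives no HADS mean, standard deviation, reliability or expected change. Every distributional input below is an assumption; only the cut of 8, the 40 patients, the 1:1 allocation and the 5% level come from the document.

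**Formula.** Let the source population have mean m and standard deviation SD, and let r be the test-retest correlation, with no true change. With a continuity-corrected cut of 7.5:

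- a = (7.5 − m)/SD, and λ = φ(a)/(1 − Φ(a))
- mean of the selected scores = m + SD·λ
- expected fall on repetition = (1 − r)·SD·λ
- SD of change = √[(1 − r)²·SD²·v + SD²·(1 − r²)], where v = 1 + aλ − λ²

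**Middle case, subscale (m = 7, SD = 4, r = 0.8).** a = 0.125, λ = 0.3958/0.4503 = 0.879, v = 0.337.

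- Selected mean = 7 + 4 × 0.879 = 10.5.
- Fall = 0.2 × 4 × 0.879 = 0.70 points.
- SD of change = √(0.04 × 16 × 0.337 + 16 × 0.36) = √5.98 = 2.44.
- A pre-post t-test at two-sided 5% would declare a fall in about 43% of trials with all 40 patients and about 23% with one arm of 20, against a nominal 2.5% in that direction.

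**Expected fall over the assumed ranges**

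| Reading of the cut | m | SD | r | Fall (points) |
|---|---|---|---|---|
| Subscale | 6 | 4 | 0.7 to 0.9 | 1.26 to 0.42 |
| Subscale | 8 | 4 | 0.7 to 0.9 | 0.86 to 0.29 |
| Total score | 15 | 7 | 0.6 to 0.9 | 0.73 to 0.18 |

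**The planned ANOVA under no effect.** A simulation with 20 per arm and 4,000 replicates per setting compared the two ways of using the score.

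- *Same score for entry and baseline.* The time effect reached p < 0.05 in 16% to 75% of trials for the subscale rows and in 6% to 10% for the total-score row. The between-arm difference in change stayed near zero (−0.01 to +0.04 points). The group-by-time interaction rejected in 4.7% to 5.5%.
- *Separate baseline taken after the entry score, with independent measurement error.* Mean change was −0.02 to +0.01 points. The time effect rejected in 4.6% to 5.8% and the interaction in 4.4% to 5.6%.

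The artefact therefore lies wholly in the within-arm quantities, and separating the two uses removes it.

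**The case against.** **Dual use is not stated.** A reader might infer that one score certainly serves both purposes. The Protocol does not say so. Table 1 puts eligibility at Week 0, before the Week 1 HADS, and Planned interventions separates eligibility from baseline. That order could imply an earlier score, and if one exists the bias largely disappears. This objection stands, so the point is conditional. What remains is that no such score is scheduled or described.

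**The randomised comparison is protected.** A reader might infer that the trial's HADS comparison is biased. It is not. Both arms pass the same filter, and the Statistical plan speaks of differences between groups. Mean change is also common shorthand in the aims of a randomised trial, and nothing in the plan says that the time effect will be read as benefit. This stands and limits the damage, but the outcome wording leaves the uncontrolled reading open.

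**Pre-post change as evidence on rehabilitation plus CBM.** CBM belongs to standard care at this site, so the randomised contrast concerns physical activity promotion. Someone wanting a HADS result for rehabilitation with CBM could turn to pre-post change. No stated aim asks for that, so the misuse is possible but not planned.

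**Carry-over to a later trial.** A reader might infer that a biased HADS figure would feed the next trial. The Statistical plan names only steps/day as clinical data for that purpose, and it puts adherence, attendance and drop-out ahead of clinical outcomes.

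**The size may be small.** If 8 is a total score, most of the assumed source population already exceeds it and the time-effect error rate is only modestly above 5%. This stands. A fall is expected on average; it is not certain in any one trial.

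**Conclusion.** The point holds conditionally. The Protocol does not say which HADS score decides entry and which is the baseline, and on its written schedule the only candidate for both is the Week 1 score. If that score serves both uses, within-arm change and the ANOVA time effect are expected to show a fall without any treatment effect. The fall is about 0.3 to 1.3 points for a subscale cut (SD 4, mean 6 to 8, r 0.7 to 0.9) and about 0.2 to 0.7 points for a total-score cut (mean 15, SD 7, r 0.6 to 0.9). The direction follows from the selection rule; the size depends on these assumptions. The documents do not support a claim that the between-arm comparison is biased, nor that a spurious improvement is bound to appear. For a secondary outcome of a 40-patient feasibility study this is worth correcting because the correction is cheap; it does not undermine the trial.

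**What to change.** 1. Reconcile Key inclusion criteria, Planned interventions, Health-related Quality of Life and Table 1. Mark a HADS at Visit 1 (Week 0) for the entry decision only, and state whether the cut of 8 applies to the total score or a subscale.
2. Keep the Week 1 HADS as the baseline for change. It should be taken before any programme session, and the cut should not be applied to it again.
3. In Aims and Trial Outcomes, word the HADS outcome as the between-arm difference at follow-up, adjusted for baseline.
4. In the Statistical plan, label within-arm HADS change and the ANOVA time effect as descriptive and not as evidence of benefit.

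The cost is one short self-completed questionnaire at a visit that already takes place, plus a few words. Some baseline scores will fall below 8, so the baseline table will look slightly less severe than the entry rule suggests; a footnote can explain why.

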**Project plan:**

This is a single centre feasibility, single blind, parallel, randomised controlled trial. We will investigate patient adherence, acceptability of additional physical activity promotion along with Cognitive behavioural Modification by the patients and the multidisciplinary respiratory team.

**Study population:**

We will recruit 40 stable COPD patients.

**Key inclusion criteria:**

- 1) COPD confirmed by obstructive spirometry.
- 2) Clinically stable male or female COPD patients aged 40 years or older.
- 3) Optimised medical therapy
- 4) Able to provide informed consent.
- 5) HADS score of 8 or above.

**Key exclusion criteria:**

- 1) Orthopaedic, neurological or other concomitant diseases that significantly impair normal biomechanical movement patterns, as judged by the investigator.
- 2) Moderate or severe COPD exacerbation (AECOPD) within 4 weeks.
- 3) Unstable ischaemic heart disease, including myocardial infarction within 6 weeks.
- 4) Moderate or severe aortic stenosis or hypertrophic obstructive cardiomyopathy.
- 5) Uncontrolled hypertension.
- 6) Another condition likely to limit life expectancy to less than one year (principally metastatic malignancy).

**Planned interventions:**

Following confirmation of eligibility, informed consent (Appendix 1) and baseline assessment (Table 1), 40 patients will be randomised to: 1) an 8-week pulmonary rehabilitation programme according to British Thoracic Society (BTS) standards [11] or 2) 8 weeks of standard pulmonary rehabilitation alongside [10] physical activity promotion [6], (Fig. 1). Randomisation will be performed independently, with 1:1 allocation using stratification, variables: HADS (8 or above) and 6MWT (above or below 350m) [6] & [12], (Fig. 2).

*Standard Care Pulmonary rehabilitation;*

*Exercise Sessions:*

All patients will attend a group programme running twice weekly for 8 weeks (16 sessions) for approximately 50 minutes of exercise and 20 minutes of education or relaxation. The exercises include an individualised programme of aerobic (cycling and walking) and strengthening exercises were each patient would be progressed at each session as able.

*Cognitive behavioural modification (CBM):*

CBM strategies are part of standard care pulmonary rehabilitation at the Royal Victoria Infirmary. Made up of four elements: behaviour, cognition/thoughts, feelings/emotions, and physical sensations [13]. A number of techniques will be used to aid symptoms of anxiety and depression including; education on anxiety and depression and COPD, distraction techniques, breathing control and relaxation and rating achievement/pleasure of physical activities [10] (Figure 1). CBM will be administered once at study entry (week 1 for 45 min session), and three times during weeks 2, 3 and 4 for 30 min each time.

*Physical activity Promotion:*

The physical activity (PA) promotion intervention, will include: 1) a step-counter with a digital display, 2) a semi-structured interview discussing motivation issues, favourite activities, and strategies to become more active; 3) a tailored physical activity coaching plan including an individualized daily activity goal (steps/day) revised weekly. Patients' targets during the course of PR will be revised every 7 days, based on performance in the preceding week. The aim is to increase physical activity by 10% each week. The goal can be altered if required. Patients will be asked to wear the step counter during waking hours for a minimum of 8 hours after waking up on a daily basis. Patients will log their daily steps on a diary provided by the PR team. On a weekly basis, staff at the pulmonary rehabilitation programme will download manually the data from the activity monitor to keep a record. The patient's goal will be adjusted to the patient's performance of the previous week and to their willingness to increase their goal [6], (Figure 1).

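### The HADS stratification factor repeats the entry criterion, so as written it has one level and only the two 6MWT strata operate

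*Protocol*

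**What the plan says.** Key inclusion criteria, item 5, requires a "HADS score of 8 or above". Planned interventions gives the order of events: "Following confirmation of eligibility, informed consent (Appendix 1) and baseline assessment (Table 1), 40 patients will be randomised to" one of two programmes. The same paragraph then names the stratification factors: "Randomisation will be performed independently, with 1:1 allocation using stratification, variables: HADS (8 or above) and 6MWT (above or below 350m"). The 6MWT factor states both sides of its cut. The HADS factor states one side only, and that side is the entry criterion.

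No other part of the protocol gives a second HADS level, a different cut or a subscale. Neither the criterion nor the factor says whether the total, the anxiety score or the depression score is meant. The randomisation sentence refers to Figure 2, which is not reproduced in the text available. Its caption explains only these abbreviations: "PR: pulmonary rehabilitation, CBM: cognitive behavioural modification, PA: Physical activity promotion". HADS and 6MWT are explained under Figure 1.

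On timing and analysis, Health-related Quality of Life says of HADS and the St George's questionnaire: "The questionnaires will be administered within 1 week before and within 1 week after the end of the rehabilitation programme". The Statistical plan says: "Differences between groups across different time points will be assessed by a two-way ANOVA with repeated measures".

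**The concern.** A stratification factor balances the arms only if patients can fall into more than one of its levels. Here the factor uses the threshold that everyone must already have passed. A randomisation list built from this sentence would balance 6MWT and do nothing for HADS, while the trial would report itself as stratified by HADS.

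The sponsor evidently wanted HADS balanced. Change in HADS is a secondary outcome. The Summary also treats mood as relevant to engagement: "CBM addresses several behavioural barriers including anxiety, depression and physical inactivity". Baseline HADS could therefore bear on the between-arm comparison of adherence, attendance and drop-out as well.

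The planned analysis does not make up for the missing balance. The two-way repeated-measures ANOVA uses baseline HADS as one of its time points, not as a covariate. With two time points its group-by-time test is the same as comparing change scores between arms, so a chance difference at baseline carries into the HADS comparison.

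**Working it through.** The protocol states no figure for this point, so there is nothing of its own to reproduce. N = 40 is given without a derivation.

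**Inputs from the protocol.** Entry at HADS 8 or above (Key inclusion criteria). Strata of HADS 8 or above and 6MWT either side of 350 m, 40 patients, 1:1, after eligibility is confirmed (Planned interventions). This gives 40/2 = 20 per arm.

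**Assumptions, not in the protocol.** The distribution of HADS among eligible patients, the pre-post correlation r, the block size, an even split around 350 m, and independence of HADS and 6MWT.

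**Step 1: count the levels.** Among patients with HADS ≥ 8, the indicator HADS ≥ 8 is always true. This holds for the total, for one subscale, or for either subscale reaching 8, provided the criterion and the factor are read the same way.
- As written: 1 × 2 = 2 strata, averaging 40/2 = 20 patients.
- With a working two-level HADS factor: 2 × 2 = 4 strata, averaging 40/4 = 10 patients.

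**Step 2: chance imbalance with no working HADS factor.** In units of the baseline SD, the standard error of the difference in means is √(2/20) = 0.316.
- P(|difference| > 0.3 SD): 0.3/0.316 = 0.949, two-sided 0.343.
- P(|difference| > 0.5 SD): 0.5/0.316 = 1.581, two-sided 0.114.

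**Step 3: ideal median split, normal scores.** The variance within each half is 1 − 2/π = 0.363, so the standard error is √(2 × 0.363/20) = 0.191.
- P(> 0.3 SD) = 0.116.
- P(> 0.5 SD) = 0.009.

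**Step 4: realistic blocks.** Simulation of 20,000 trials of 40 patients, half on each side of 350 m, with permuted blocks in each stratum and incomplete blocks allowed:

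| Scheme | Scores | P(> 0.3 SD) | P(> 0.5 SD) |
|---|---|---|---|
| 6MWT only, blocks of 4 | normal | 0.343 | 0.113 |
| 6MWT × HADS median, blocks of 4 | normal | 0.144 | 0.015 |
| 6MWT × HADS median, blocks of 2 | normal | 0.133 | 0.013 |
| 6MWT only, blocks of 4 | exponential | 0.337 | 0.109 |
| 6MWT × HADS median, blocks of 4 | exponential | 0.201 | 0.039 |

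A working split reduces the imbalance but does not remove it, and it helps less when scores above the cut are strongly skewed.

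**Step 5: effect on the HADS change comparison.** With equal variances, a baseline difference of d shifts the expected between-arm difference in change by d(1 − r) in size. For d = 0.5 SD:
- r = 0.3: 0.5 × 0.7 = 0.35 SD
- r = 0.5: 0.5 × 0.5 = 0.25 SD
- r = 0.7: 0.5 × 0.3 = 0.15 SD

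**Step 6: precision.** The variance of the change-score estimate relative to the baseline-adjusted estimate is 2/(1 + r) = 1.54, 1.33 and 1.18 for the same three correlations.

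**The case against.** **Other readings could give the factor two levels.** Table 1 puts the eligibility check at visit 1 and the quality of life assessment, which includes HADS, at visit 2, so a second reading could fall below 8. Entry might be on one HADS score and stratification on another. Figure 2 might show the levels, and its abbreviation list is weak evidence that it does not. None of these readings has support in the text. A below-8 stratum from a second reading would contain only patients who no longer meet criterion 5. If the figure or a subscale rule does define levels, the sentence under Planned interventions still needs to say so. What stands is that the unseen figure cannot be ruled out, so the finding concerns the rule as written.

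**The consequence is small.** The Statistical plan puts adherence, attendance and drop-out ahead of clinical outcomes. HADS change is one of four secondary outcomes, both arms receive CBM, and nothing in the protocol shows that HADS severity above 8 predicts adherence. Even a 0.5 SD imbalance, which has an 11% chance, shifts the change comparison by less than one standard error: √(2 × 2(1 − r)/20) = 0.37, 0.32 and 0.24 SD for r = 0.3, 0.5 and 0.7, against shifts of 0.35, 0.25 and 0.15 SD. Averaged over randomisations, the analysis's standard error already covers this. All of that stands and limits the size of the point. It does not make the factor work.

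**Baseline adjustment is a separate matter.** Whether to adjust is commonly left to an SAP, and adjusting would gain precision even with perfect stratification. That is fair. Adjustment is raised here only because it recovers what the stratification was meant to provide, not as an omission from the protocol.

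**Conclusion.** The concern holds. The HADS factor and the entry criterion use the same cut, so the design as written is stratified by 6MWT alone. This follows from the two passages and does not depend on any distributional assumption.

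In practice the loss is modest: unintended chance imbalance in baseline HADS, with no bias in the allocation. How far a working split would help rests on assumed score distributions and block sizes, and the effect on the HADS change comparison rests on an assumed correlation. The primary outcome, adherence to activity trackers, is largely measured within the arm that receives the step counter and is little affected. The sentence should be corrected because it fixes a rule that cannot do what it is there to do, and a later analysis plan cannot restore balance that the list never imposed.

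**What to change.** Before the randomisation list is generated, state which HADS score (total, anxiety or depression) and which reading serve for entry and for the stratum. Then do one of the following.

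- **Keep HADS as a factor.** Replace the present cut with levels that both occur among eligible patients, for example a cut at their expected median or a split by which subscale reaches 8, and use small blocks. The protocol gives no HADS distribution, so a median cut needs a figure from the sponsor's own clinic data. With four strata of about 10 patients, simulated arm sizes stay within 19 to 21 in about 92% of trials with blocks of 4 and about 98% with blocks of 2.
- **Drop HADS as a factor.** This leaves the allocation as it would be under the present wording. Adjust the between-arm outcome models for baseline HADS. This is also the route if recruitment has already started.

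The first option costs one line in the protocol and one in the list specification. The second adds a sentence to the Statistical plan. Neither needs new data, since baseline HADS is already collected.
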